### 4.0 Data Analysis (Aims 1-3)

Data on all patients randomly assigned to the intervention or control groups will be analyzed on an intention-to-treat basis. Deviations from randomized allocation will be reported. Summary statistics based on mean, standard deviation or frequency will be used to characterize the sample distribution of each arm. Proper transformations will be investigated and taken if the sample distributions of continuous variables violate the normality assumption. For Aims 1-3, generalized linear mixed models (GLMMs) will be used to test the differences between the two arms since cluster randomized control design is used. There are four components in GLMMs: outcome variable, fixed effects, random effect, and link function. The fixed effects include explanatory variable and covariates. In this study, all three aims have the same explanatory variable which is a binary variable indicating the arm to which women are assigned. The study sites, gestational age, and women's demographic variables such as education or literacy, marital status, pregnancy history, and medical history will be added to the GLMMs as covariates to increase the precision of estimates. The random effect is the 14 facilities. In this study, a random intercept model will be used to account for the cluster effect. The outcome variables and link functions in GLMMs depends on aims and are described below. The construct of GLMMs is to test if the explanatory variable is significant at 0.05 level using likelihood ratio test.

For **Aim 1** to quantify differences in the recognition of pregnancy and newborn danger signs and knowledge of recommended action steps, the BPCR Index will be measured at enrollment and third trimester. We will add baseline data as covariates. The logit link function will be used for each binary BPCR question to test the efficacy of the group-based ANC method. The identity link function will be used when the outcome variable is a summary statistic of the BPCR Index. When the p-value of the explanatory variable is less than 0.05, we will declare a significant difference between the two arms. Average changes in BPCR summary statistics or odds ratio in each question will be used to quantify the effect of the group-based ANC intervention.

For **Aim 2** of assessing behavioral differences in care-seeking patterns between the two arms, the outcome variables are number of attendances in ANC visits, facility birth, and postnatal/partum care. For the attendance outcome variable, identity function will be used. For facility birth or postnatal/partum care, the logit link function is used. When the p-value of the explanatory variable is less than 0.05, we will declare a significant difference between the two arms. The effect of group-based ANC on attendances is quantified by the average difference. The effects of group-based ANC on facility birth and postnatal/partum care are quantified by odds ratio. For the secondary outcomes in aim 2, the logit or identity links will be used in the way similar to the primary outcomes.

For **Aim 3** to evaluate the clinical outcomes of mothers and their newborns, the outcome variables are maternal pregnancy-related morbidities and newborn birth status. For maternal morbidities, the logit link function is used. Since the newborn birth status is classified into three categories (stillbirth, live birth, and early neonatal mortality), cumulative logit link function is used. When the explanatory variable is significant at 0.05, the effect of group-based ANC on maternal pregnancy-related morbidities and newborn birth status are interpreted using odds ratio. We will illustrate the difference between outcomes using odds ratios for each pair of newborn birth status. The secondary outcomes are analyzed similarly using identity or logit link functions.

For the multiple outcomes in the same family, we will conduct direct inference using the Holm's multiple testing procedure to control familywise error rate at 0.05 level. The GLMM analysis will be carried out using lme4 package from R software. All findings will be reported using the Consolidated Standards of Reporting Trials (CONSORT) statement as a guide. Full transparency will be provided when reporting experimental details so that others may reproduce and extend our findings. We will register the study with clinicaltrials.gov and disclose all demographic and baseline characteristics, as well as primary and secondary outcomes.

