### **3.0 Research Methods and Study Design**

To accomplish our aims we propose a cluster randomized controlled trial (cRCT) in the Eastern District of Ghana. The study is designed in collaboration with the Dodowa Health Research Center under the direction of [name] (Co-PI). Health facilities were selected based the number of deliveries and average gestational age of women in each facility and matched so that each pair of facilities are similar to each other with regard to these matching factors. For each pair of facilities, one will randomly be assigned to group ANC (intervention) and the other to routine, individual ANC (control). The locations of the chosen facilities ensure that participating facilities will be far enough apart to minimize the likelihood of cross-group contamination. The unit of randomization is the health facility stratified by site and gestational age. Cluster randomization will be produced through nbpMatching package from R software. During the study, 1680 participants will be randomized into 120 groups of 12 to 14 women of the same gestational age at the cluster site. This will result in approximately 8-10 groups per site during the study period.

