### **3.4 Process Evaluation**

We will concurrently conduct a process evaluation to identify and document patient, provider, and system barriers and facilitators to program implementation. Using both quantitative and qualitative methods, we will identify potential and actual influences on the quality and conduct of the program's operations, implementation, and service delivery.

**Data Collection (Process Evaluation):** Process evaluation data will be collected via audiotaped semi-structured interviews with facility staff and women participating in GANC. Process evaluation data will include an assessment of both providers' and women's perceptions.

All midwives (providers) involved in the intervention arm (GANC) will be asked to participate in the process evaluation. Midwives will be approached by the RA at the end of the 7th group meeting and asked if they are interested in providing feedback about group care. Those willing to participate will be taken through a consent process before the first interview begins. Each midwife will be interviewed at two random times and each interview will last approximately 40 minutes. A structured interview using open-ended questions will be conducted to explore the midwife's perceptions of group versus standard ANC, barriers to implementation, challenges to integrating it into the existing clinic workflow, and strategies that have helped with implementation. Interviews will be audiotaped (with permission from the participant) to ensure accuracy of responses; midwives can refuse to be audiotaped yet continue with the interview. The RA will write short answer responses on a data collection form. Audio tapes will be transcribed and will be de-identified; tapes will be destroyed immediately after transcription. We have 7 health facilities randomized to the intervention arm and 2 to 4 midwives at each facility; As each midwife may be interviewed twice, we expect approximately 56 midwives may participate in the process evaluation.

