### 3.7 Randomization

There are 14 sites in the study. We randomized these 14 sites into the control group and the intervention group. To improve the balance between the two groups and improve the efficiency of estimating intervention effect, we used the facility type, district of site, and ANC registrant numbers in 2018 to conduct matched randomization. The randomization process were carried out using nbpMatching package from R software.

Control Sites				Intervention Sites			
Facility	Facility Type	District	ANC 2018	Facility	Facility Type	District	ANC 2018
Adawso	Health Center	Akuapim North	403	Akuse	Hospital	Lower Manya Krobo	378
Abiriw	Clinic	Akuapim North	322	Adkukrom	Health Center	Akuapim North	299
Tetteh Quarshie	Hospital	Akuapim North	654	Atua	Hospital	Lower Manya Krobo	715
St Martin's	Hospital	Lower Manya Krobo	1081	Nsawam	Hospital	Nsawam	4930
Nsawam	Health Center	Nsawam	901	Adoagyiri	Health Center	Nsawam	817
Djankrom	Health Center	Nsawam	295	Klo Agogo	Polyclinic	Yilo Krobo	237
Nkurakan	Health Center	Yilo Krobo	469	Somanya	Polyclinic	Yilo Krobo	616

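### The likelihood ratio test of arm has no small-sample correction for 14 randomised facilities, so the stated 5% level is not secured

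*Combined protocol and SAP*

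**What the plan says.** Section 4.0 (Data Analysis, Aims 1-3) fits generalized linear mixed models with arm as the explanatory variable. On clustering it says: "The random effect is the 14 facilities. In this study, a random intercept model will be used to account for the cluster effect". On the test it says: "The construct of GLMMs is to test if the explanatory variable is significant at 0.05 level using likelihood ratio test". The 0.05 rule is repeated for each aim, and Holm's procedure is applied within families of outcomes that are not listed. The software statement is "The GLMM analysis will be carried out using lme4 package from R software".

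Section 3.7 gives the number of randomised units: "There are 14 sites in the study. We randomized these 14 sites into the control group and the intervention group". Section 3.4 confirms the split: "We have 7 health facilities randomized to the intervention arm". Section 3.7 also says that "we used the facility type, district of site, and ANC registrant numbers in 2018 to conduct matched randomization". Section 4.0 has no pair term. It does add the study sites as a covariate, without saying whether this means the facilities, the districts or something else.

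The plan states no reference distribution for the test, no interval method, no ICC and no power calculation.

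**The concern.** Arm varies only between facilities. However many women are enrolled, an arm-only model leaves 14 - 2 = 12 degrees of freedom for judging the arm effect. The usual likelihood ratio test refers its statistic to a chi-square distribution that is exact only as the number of clusters grows. The maximum likelihood fit behind it also underestimates the between-facility variance, and more so as facility-level terms are added.

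If the p-values are too small, differences will be declared significant more often than the plan says. Holm cannot correct this, because it controls familywise error only when the p-values it receives are valid. The same test governs the claims of all three aims, so the reference distribution has to be right before results are seen.

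**Working it through.** **Inputs from the documents.** Nominal level 0.05 (section 4.0); 14 facilities, 7 per arm (sections 3.7 and 3.4); 1680 women (section 3.0), hence 1680/14 = 120 per facility on average; four districts (section 3.7 table).

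**Assumptions.** The documents give neither the ICC nor the share of facility variance common to a matched pair, so both are varied below. The chi-square(1) reference is also assumed, as the usual default.

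**1. Exact level, balanced facilities.** When the between-facility variance is estimated above zero, LRT = 14 × ln(1 + t²/df), where t is the ordinary between-facility t statistic and df = 14 minus the number of facility-level fixed effects, counting intercept and arm. Rejecting when LRT > 3.841 is the same as rejecting when |t| > √[df × (exp(3.841/14) − 1)]. Since exp(3.841/14) − 1 = 0.3157, the arm-only cut-off is √(12 × 0.3157) = 1.946. The correct 5% value on 12 df is 2.179.

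| Facility-level fixed effects | df | LRT's effective cut-off | Correct t value | Actual level |
|---|---|---|---|---|
| Intercept, arm | 12 | 1.946 | 2.179 | 7.54% |
| plus two covariates | 10 | 1.777 | 2.228 | 10.6% |
| plus four districts (3 terms) | 9 | 1.686 | 2.262 | 12.6% |
| plus seven pairs (6 terms) | 6 | 1.376 | 2.447 | 21.8% |

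The plan's 5% is not reproduced in any row. At Holm's first step for three outcomes (0.05/3 = 1.67%, chi-square cut-off 5.731), the 12-df cut-off is √[12 × (exp(5.731/14) − 1)] = 2.464, an actual level of 2.98%. On 9 df it is 6.16%.

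**2. Dependence on ICC and matching.** Gaussian random-intercept model, arm only, 14 × 120 women, 100,000 simulated trials per setting:

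| Facility variance shared within pairs, pairs ignored | ICC 0 | 0.001 | 0.005 | 0.01 | 0.02 | 0.05 | 0.1 | 0.2 |
|---|---|---|---|---|---|---|---|---|
| None | 4.0% | 4.7% | 6.3% | 7.1% | 7.5% | 7.6% | 7.5% | 7.5% |
| 25% | 3.8% | 4.4% | 5.3% | 5.4% | 5.3% | 4.9% | 4.7% | 4.7% |
| 50% | 3.9% | 4.2% | 4.2% | 3.9% | 3.3% | 2.8% | 2.4% | 2.1% |

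**3. Logit outcomes.** Random-intercept logistic model, 2,000 simulated trials per setting, standard error about 0.4 to 0.6 points, no pair correlation:
- ICC 0.05: 8.0% (event rate 50%), 6.7% (73%), 7.5% (73%, unequal facility sizes), 6.2% (2%).
- ICC 0.01: 6.6% (73%).
- ICC 0: 3.4% (50%), 4.1% (2%).

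The cumulative-logit model for birth outcome was not simulated.

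**4. Does a t reference repair it?** In the Gaussian simulations, a t-test on 12 df held 4.95% to 5.04% at every ICC from 0 to 0.2 when pairing explains nothing. When pairing explains 25% or 50% of facility variance and is ignored, it ran at 1.2% to 4.9%. A Wald z test with REML is no repair: its level on 12 df is 7.36%.

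**The case against.** The strongest reply is that the direction of the error is not settled. Section 3.7 says the facilities were matched to improve efficiency, and the model has no pair term. If matching works and is ignored, the same test is close to nominal or conservative (2.1% to 5.4% above); if the ICC is near zero, the level is about 4%. This stands. A reader might infer that the real type I error is 7.5% to 8% for every claim in the trial. The documents do not support that, because they fix neither the ICC, nor the effect of matching, nor the facility-level covariates. Nor do they support the inference that significance is over-declared for every outcome.

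A reader might also infer that the confidence intervals will be too narrow. The plan names p-values, mean differences and odds ratios but no interval method, so this would be true only of intervals built on the same large-sample reference.

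It is fair, too, that the chi-square reference is inferred: a parametric-bootstrap likelihood ratio test would fit the plan's wording.

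None of this rescues the plan. The low levels depend on unknowns, or on an analysis that ignores its own design and gives up power. Effective matching cannot be assumed: if the rows of the section 3.7 table are the pairs, which the text does not say, only one of seven agrees on both facility type and district, and one sets 1081 registrants against 4930. The study-sites covariate points the other way: read as the four districts it gives 12.6%, and read as the 14 facilities it leaves arm aliased and untestable.

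**Conclusion.** Wrong as written. The plan states a 5% level, and the test it names, with its usual reference and 14 facilities, does not secure it. The central figure is about 7.5%, for an arm-only model with an assumed ICC of about 0.02 or more and no gain from matching. Facility-level fixed effects raise it; a near-zero ICC, or effective matching left out of the model, brings it to about nominal or below.

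The lack of a small-sample method and the balanced-cluster arithmetic are certain. Where in this range the trial will fall cannot be determined from the documents. For rare binary outcomes the evidence is one event rate (2%), and for the three-category birth outcome the size of the error is unquantified.

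**What to change.** Amend section 4.0 before the analysis.

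- **Identity-link outcomes:** REML with Kenward-Roger F tests of arm.
- **Logit and cumulative-logit outcomes:** a t reference with between-facility df (14 minus the number of facility-level fixed effects, including intercept and arm), or a parametric-bootstrap likelihood ratio test.
- **Intervals:** build any that are reported on the same reference as the test.
- **Pairs and sites:** list the matched pairs and state in advance whether they enter the model. Define the study-sites covariate. Do not enter the 14 facilities as fixed effects.
- **Check:** a within-pair permutation p-value. There are 2⁷ = 128 allocations, so the smallest two-sided p is 2/128 = 0.0156. That passes Holm's first step for three outcomes (0.0167) but not for four (0.0125), so the check is useful at that step only in families of three or fewer. The families must therefore be listed.

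**Cost:** SAP wording and a few lines of R, with no new data. For the arm-only model the critical value rises from an effective 1.946 to 2.179, about 12%. It rises by about 25% with two facility-level covariates (2.228/1.777) and 78% with pair terms (2.447/1.376). If effective pairing is left out of the model, the 12-df t-test is conservative and loses power, so the pair decision should be made together with this change.

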### **1.1 Ghanaian Context**

In 2015, the maternal mortality ratio in Ghana was estimated at 319 per 100,000 live births – placing a woman’s lifetime risk of maternal death at 1 in 74, compared to 1 in 3,800 in the United States. In 2014, while 87.3% of women in Ghana surveyed had attended the minimum standard of 4 antenatal care (ANC) visits, 27% gave birth alone or with a non-skilled attendant. Sixty-eight percent of all deaths among children under age 5 in Ghana happen before a child’s first birthday, with 48% of deaths occurring in the first month of life - making the first 28 days in an infant’s life crucial for survival. Only 22.8% of newborns received the recommended postnatal check-up within the first two days of life between 2012-2014 in Ghana. It should be noted that since 2008 there has been only a marginal decline (3%) in neonatal mortality within Ghana. Ghana is now one of 24 priority countries targeted by the United States Agency for International Development (USAID) to improve maternal and child health and end preventable deaths.

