### Primary Outcomes

- Attendance at 4+ ANC visits
- Facility birth
- Four postnatal/postpartum check-ups for both mother and newborn in the first 6 weeks after birth

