## Measures

Time Point	Domain	Data collection
T0 – Baseline	Demographic Characteristics (Age, gravida, living children, marital status, age at marriage, pregnancy history, medical history)	Face-to-face Survey
	Self-efficacy	
	Recognize problems and understands health information	Face-to-face Survey
	Care-seeking history	Face-to-face Survey
	Educational Background	
	Level of Education	Face-to-face Survey
	Prior Knowledge	
	Ability to identify danger signs/BPCR	Face-to-face Survey
	Health Literacy Skills (understanding, engagement with health system)	Face-to-face Survey
	Ecological Influences (social support, community and family resources)	Face-to-face Survey
T1 – Third trimester	Comprehension of Stimuli (identification of danger signs, BPCR)	Face-to-face Survey
	Self-determination	
	Intent to use family planning / preparation for birth	Face-to-face Survey
	Two or more tetanus toxoid vaccines / Completion of ITP 2 malaria prophylaxis	ANC Card
T2 – Post birth	Clinical Health Related Outcomes (Place of birth, hemoglobin levels, newborn birth weight, maternal & newborn morbidities, stillbirth, postpartum visit within 2 days post birth)	ANC Card
	Self-determination	
	Attendance at 4 or more ANC visits	ANC Card
	Adherence to care - Number of ANC Visits	ANC Card
	Health Related Behavior (Maternal and newborn postpartum visits)	Survey
	Clinical Health Related Outcomes (Perinatal mortality (<7 days), maternal morbidities)	ANC Card
T3 – Six months postpartum	Health Related Behavior (Uptake of modern family planning, exclusive breastfeeding, 4 postnatal check-ups completed on both mother and newborn in first 6 weeks)	Survey via phone
	Clinical Health Related Outcomes (Neonatal mortality(<28 days), maternal morbidities)	Survey via phone
T4 – One year postpartum	Health Related Behavior (Repeat pregnancy)	Survey via phone
	Clinical Health Related Outcomes (Infant immunized per EPI schedule; maternal morbidities)	Self-report Survey via phone

During all visits midwives will record Clinical Health Related Outcomes (Place of birth, hemoglobin levels, newborn birth weight, maternal & newborn morbidities, stillbirth, postpartum visit within 2 days post birth) on the women's ANC card. These data will be collected by the RA during all study visits except baseline.

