### **3.5 Intervention - Description of the Model for Group Antenatal Care**

The group ANC model was modified from a curriculum initially developed by the American College of Nurse Midwives to mobilize communities in low-resource countries for early problem identification of pregnancy related problems and referral. Using an iterative process with Ghanaian providers, pregnant women, and stakeholders as well as content experts from the U.S. to ensure local and cultural relevance and the WHO Standards for Maternal and Neonatal Care, the group ANC model was developed and tested for acceptability and feasibility by [name] and her Ghanaian team for the first time in a clinical setting in Ghana. At the core of the model is a negotiation process that acknowledges some health messaging may be in conflict with cultural beliefs. The model allows participants to incorporate safe, feasible, and culturally acceptable health beliefs into self-care actions by being inclusive of traditional practices that are not

harmful. Participants and the facilitator ‘agree’ on safe and acceptable actions within the context of the setting that are then practiced by the group.

The intervention consists of nine meetings; one individual meeting and eight group meetings. At the initial ANC visit, women are assigned to a small groups with 12-14 women of similar gestational age. Women meet individually with the midwife and the standard complete history and physical exam as well as lab tests are completed; group visits start at the second ANC visit. Prior to the start of each group, blood pressure, weight, and a urinalysis are measured for each woman. The midwife, health facility staff member, and patients then sit in circle facing one another for a 60-90 minute facilitated discussion. The health facility staff member will assist the midwife with group activities. The model uses strategies such as story-telling, peer support, and demonstration and teach-back to enhance its effectiveness. Health literacy is incorporated as an integral part of clinical practice within the model – not as an add-on to care.

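### Aim 2 declares attendance at four or more antenatal visits as a primary outcome, but Section 4.0 specifies an analysis only for the number of visits

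*Combined protocol and SAP*

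**What the plan says.** Section 2.0 gives Aim 2 three primary outcomes. The first is "Attendance at 4+ ANC visits", which each woman either meets or does not. The others are facility birth and completion of four postnatal/postpartum check-ups.

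The Measures table in Section 3.3 takes two attendance items from the ANC card at T2. One is "Attendance at 4 or more ANC visits". The other, on its own line and labelled as adherence, is the number of visits.

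For Aim 2, Section 4.0 states that "the outcome variables are number of attendances in ANC visits, facility birth, and postnatal/partum care". It then assigns the methods:

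- Attendance: "For the attendance outcome variable, identity function will be used", and "The effect of group-based ANC on attendances is quantified by the average difference".
- The other two primaries: "For facility birth or postnatal/partum care, the logit link function is used", with odds ratios.
- Secondary outcomes: a closing sentence allows either link. It does not extend to primaries.

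All models are mixed models with a random intercept for facility, tested at 0.05 by likelihood ratio. Holm's procedure is applied to outcomes in the same family.

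**The concern.** The declared primary asks whether more women reach the four-visit standard. The specified analysis asks whether women attend more visits on average. Visits beyond the fourth raise the mean and leave the four-or-more rate unchanged, so the mean can move when the declared outcome does not.

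Two things are at stake. Followed as written, the plan tests a variable that Section 2.0 does not name as primary, and a significant result could be read as success on one that it does. And because both variables are collected and each has some claim to the primary position, the choice could be made after the results are known. For the same reason, the set of hypotheses entering Holm's procedure is not fixed.

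**Working it through.** **1. The sections side by side**

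| Place | Attendance variable | Type | Analysis given |
|---|---|---|---|
| Section 2.0, Aim 2 primary | four or more visits | yes/no | none |
| Section 3.3, Measures, T2 | four or more visits, and number of visits | both | not applicable |
| Section 4.0, Aim 2 | number of visits | count | identity link, mean difference |

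Section 3.3 lists the two separately, so the wording in Section 4.0 cannot easily be read as shorthand for the binary item. This mismatch needs no arithmetic. The steps below only show that it can matter.

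**2. Design figures**

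Section 3.0 gives 1680 women in 120 groups of 12 to 14, which reproduces at the upper size: 120 × 14 = 1680. With 14 sites (Section 3.7), 7 of them in the intervention arm (Section 3.4), this is 1680/14 = 120 women per site and 7 × 120 = 840 per arm. No power calculation, ICC, SD or dropout rate is stated.

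**3. Can the two measures diverge?**

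*Constructed extreme.* Take 87.3% at four or more (Section 1.1). If each of these women makes one extra visit and nobody else changes:

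- change in mean = 0.873 × 1 = 0.87 visits
- change in four-or-more rate = 0 points

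Could the test of means detect 0.873 visits? Assume an SD of 2 to 3 visits, with SE = SD × √(2 × DE/840) and DE = 1 + 119 × ICC.

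| Assumed ICC | DE | SE (SD 2; SD 3) | Power, normal approximation |
|---|---|---|---|
| 0.01 | 2.19 | 0.144; 0.217 | 98–100% |
| 0.05 | 6.95 | 0.257; 0.386 | 62–92% |

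With 14 clusters the normal approximation is optimistic. Taking power as P(T₁₂ > 2.179 − 0.873/SE), the ranges become about 96–100% and 53–88%.

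*Milder case.* Suppose counts are Poisson with P(X ≥ 4) = 0.873, so the mean is 6.29. One more visit on average gives a mean of 7.29 and P(X ≥ 4) = 0.932, a rise of 5.9 points. Here both measures move, but the binary one only modestly.

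**4. What the binary outcome could detect**

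Take p₀ = 0.873, 80% power, two-sided 0.05, t with 12 df, 120 women per site and no dropout. The multiplier is 2.1788 + 0.8726 = 3.0514. With each arm's own variance, solve

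p₁ − p₀ = 3.0514 × √{[p₀(1 − p₀) + p₁(1 − p₁)] × DE/840}

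| Assumed ICC | DE | p₁ | SE | Detectable difference |
|---|---|---|---|---|
| 0.01 | 2.19 | 0.937 | 0.0210 | 6.4 points |
| 0.02 | 3.38 | 0.950 | 0.0252 | 7.7 points |
| 0.05 | 6.95 | 0.975 | 0.0334 | 10.2 points |

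If 87.3% applied, the most the rate could rise is 100 − 87.3 = 12.7 points. This is an unadjusted comparison of proportions, not the planned likelihood ratio test, so it is a guide to scale only.

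**The case against.** **The mixed-model framework is general and the binary item is collected, so a logit model could simply be fitted.** This stands in part. It would be wrong to say that the declared primary will never be tested; what can be said is that no test is specified for it. That remains a gap, because Section 4.0 assigns attendance to the identity link.

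**The figures rest on outside assumptions.** This also stands. The 87.3% is a national survey figure, whereas trial women are low-risk and enrolled at a facility before 20 weeks (Section 3.2). The one-extra-visit case is constructed, and the ICCs and SDs are assumed. A reader who gave both arms the variance at 87.3% would get 7.3, 9.1 and 13.1 points. The last exceeds the 12.7 available and would wrongly suggest that 80% power is out of reach at ICC 0.05. The variance falls near the ceiling, so the smaller figures in the working apply.

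**Only one primary is affected.** It is one of three for Aim 2 and one of eight across the aims, and Holm's procedure limits what one outcome can claim. That restricts the reach of the problem without removing it.

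**A stronger reading is tempting: that the count is driven by the intervention's own schedule.** Section 3.5 says "The intervention consists of nine meetings; one individual meeting and eight group meetings", and group meetings serve as ANC visits. The documents do not support the inference. They give no number of control-arm visits. Section 3.6 says follow-up visits are the same in both conditions, which may mean study contacts or ANC visits. The structured-observation text in Section 3.4 refers to seven group visits where Section 3.5 has eight, and these must be reconciled. Group meetings also count towards four or more, and higher attendance is part of what Aim 2 sets out to measure. At most, visits after the fourth raise the mean but not the four-or-more rate.

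**Conclusion.** The concern holds as a mismatch between Sections 2.0 and 4.0: a declared primary outcome has no specified analysis, and a variable that Section 2.0 does not name is analysed in its place. This follows from the text alone.

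That the measures can lead to different conclusions is shown by illustration (a mean shift of 0.87 visits with no change in the rate, at a background of 87.3%), not estimated for this trial. It is enough to say that a significant mean difference would not establish the declared primary. The documents do not show that the count will be inflated, that the two results will differ, or that the binary measure will go untested. The detectable differences of about 6, 8 and 10 points depend on the assumed ICCs, equal site sizes, no dropout and the national rate.

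**What to change.** Give one attendance measure the primary label in both sections, before outcome data are seen.

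- **If four or more visits stays primary:** in the Aim 2 paragraph of Section 4.0, specify the logit-link mixed model with an odds ratio for four or more visits (yes/no). Place it in the Holm family with the other Aim 2 primaries, and label the visit count supportive, keeping its identity link and mean difference.
- **If the sponsor prefers the count:** change the Aim 2 primary in Section 2.0 to the number of ANC visits, and label the four-or-more measure supportive.

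Either route costs only wording, since both items are already taken from the ANC card at T2. The first may also cost power if attendance is near its ceiling, as the detectable differences in the working indicate. That is a reason to decide now, not a reason to leave the choice open.
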